- Include sample manifest with participant IDs and aliquot details

8. Plasma Analysis and Sharing

- The samples will be received by the UCL Biomarker Factory, who will complete the biomarker analysis using Quanterix Simoa® ALZpath pTau 217.
- A research database with pTau217 levels and the participant ID will be created and shared with the CI via the share function on MS SharePoint, which will include multi-factor log-in procedures, access control and an expiration.

9.4. Data Storage, Retention and Archiving

All aspects of the CoCoA-PAD data storage, retention and archiving strategy are compliant with the University of Plymouth's [Data Retention and Erasure Policy](#).

Personal Identifiable Information

Personal identifiable information will be stored in a REDCap database, which will be stored securely and separately to the site file. This data will only be accessible to the CI, [name], [name], [name], and [name]. Personal identifiable information will be stored until the REDCap research database has been cleaned, audited and finalised, after which, the personal identifiable information database will be permanently deleted.

REDCap Research Database

As outlined in section 9.3: Data Collection and Processing, participant's demographic and health data, neuropsychological assessment data, MRI data, plasma biomarker data, and post-processed speech data, will be transferred to the anonymous research database. This

The CoCoA-PAD database, developed in REDCap, has been designed to fully align with the principles outlined in the Good Clinical Data Management Practices (GCDMP) standards. The database structure is underpinned by a version-controlled data dictionary that defines all variables, field types, validation rules and export classifications. Data integrity will be supported through field-level validation (i.e., to ensure the data is entered in the correct format and within specified parameters), automated logic checks, audit trails, and restricted, role-based access controls. All modifications to the database and records will be logged, providing a complete audit trail in compliance with regulatory expectations. The database is hosted on a secure, university-managed REDCap instance, with encryption at rest and in transit, daily backups, and alignment with institutional information governance policies.

To ensure the data can be reused by external researchers, the CoCoA-PAD database includes a comprehensive metadata structure at both the variable and project levels. Each variable is clearly defined in REDCap's data dictionary. In addition, project-level metadata will be provided alongside the dataset, including a README file explaining study aims, variable naming conventions, missing data codes, and scoring instructions, and a metadata guide mapping variable to clinical constructs and study timepoints. This approach ensures that de-identified data shared with external teams will be accompanied by all the necessary contextual information for independent analysis, promoting transparency, reproducibility, and alignment with Findable, Accessible, Interoperable, and Reusable (FAIR) data principles.

At the conclusion of data collection for the CoCoA-PAD study, the database will undergo a formal closure process to ensure data integrity, regulatory compliance, and readiness for analysis. The datasets will be reviewed by a database specialist with the Peninsula Clinical Trials Unit (PenCTU) at University of Plymouth, who will review it against best practice guidance and the procedure outlined above. Any issues identified by the database specialist will be addressed. Prior to locking the database, a structured internal audit will be conducted by the study team to verify the accuracy, completeness, and consistency of the dataset. This will involve resolving all outstanding data queries, reviewing audit trails, checking for missing or anomalous values, and confirming that data entry aligns with the study protocol and consent

requirements. Once all discrepancies have been addressed and all fields are verified, the REDCap database will be transitioned to read-only status, locking all data fields to prevent further modification. The final dataset, along with a complete version-controlled data dictionary, codebook, and audit documentation, will be exported and securely archived on the University of Plymouth's institutional repository – (Plymouth Electronic Archive and Research Library (PEARL)).

Raw Audio Data

Raw audio files in mp4 format will be stored in a separate access-controlled and secure SharePoint folder on the site file, with access restricted only to the CI, [name] and [name]. All audio files will be stored with AES-256-bit encryption, due to the identifiable nature of audio recordings. Each audio file is estimated to range from 60 to 100 megabytes, and therefore in total, this folder will be approximately 7.2 to 12GB in size.

Raw audio will be stored securely for 10 years after data collection, in compliance with the University of Plymouth's Data Retention and Erasure Policy (version 3.0).

Raw Demographic and Health Information

Raw demographic and health data will be downloaded from the Gorilla Experiment Builder website in .xlsx format (Microsoft Excel spreadsheet). The raw data file will be encrypted with a strong password (three random words, as recommended by the National Cyber Security Centre, <https://www.ncsc.gov.uk/collection/top-tips-for-staying-secure-online/three-random-words>).

Target data will be extracted from the .xlsx file into the research database on REDCap. The raw demographic and health .xlsx files will be stored in an access-controlled folder on the site file and retained for a period of 10 years. After this period, the raw data will be permanently deleted.

Raw Neuropsychological Assessment Data

Neuropsychological assessment data will be collected using the Gorilla Experiment Builder 2.0. The storage and retention of the data from both platforms follow an identical procedure. Raw cognitive assessment data will be downloaded from the Gorilla Experiment Builder website in .xlsx format (Microsoft Excel spreadsheet) and transferred to a secure and access-controlled folder on the CoCoA-PAD site file. The raw data file will be encrypted with a strong password (three random words, as recommended by the National Cyber Security Centre, <https://www.ncsc.gov.uk/collection/top-tips-for-staying-secure-online/three-random-words>).

Target data will be extracted from the .xlsx file into the research database on REDCap. The raw Neuropsychological Assessment Data .xlsx files will be stored in an access-controlled folder on the site file and retained for a period of 10 years. After this period, the raw data will be permanently deleted.

Raw MRI Imaging Data

Raw anonymised MRI data is archived in original DICOM format on the DICOM server (AET: ORTHANC-Lin2) located on the University premises and connected to the University network. The MRI raw data is stored securely for at least 10 years. The BRIC Data Management Policy v1 (26/03/2021) provides a more detailed description of the BRIC procedures for data storage, retention and archiving).

Raw Blood Samples

Plasma samples will be sent to UCL's Biomarker Factory for analysis. The Biomarker Factory will analyse the plasma samples, and produce an anonymised dataset, which will include the participants' ID codes and pTau217 results. The plasma samples will not be used for any additional research and will be destroyed using bleach once the analysis has been completed and verified.

The UCL Biomarker Factory retain an encrypted version of the anonymous database on a locked Biomarker Factory channel on MS Teams for a period of at least ten years. This database will be transferred securely using MS Teams to the CoCoA-PAD CI, who will transfer the results into the REDCap database, and store this database in an access-controlled folder on the CoCoA-PAD site file for a period of at least 10 years.

9.5. Access and Data Sharing

Access to identifiable data, audio recordings or raw data will be limited to named members of the study team. This data will not be shared with any external partners, nor any members on the project team, unless explicitly stated in sections 9.3 and 9.4.

The CoCoA-PAD dataset will be shared in accordance with principles from the Open Science movement, supporting transparency, reproducibility, and wider scientific collaboration. The full research database will be deposited in a trusted institutional or subject-specific data repository, such as PEARL. Requests for access to the full anonymised database will be reviewed on a case-by-case basis. Access will be granted to qualified researchers who provide evidence of an appropriate data management plan, including commitments to ethical use, secure storage, and compliance with relevant data protection regulations. Requests for access will be reviewed by the sponsor and CI to ensure appropriate controls are in place. A data availability statement, which outlines this plan, will be included in all research publications.

Most of the sample will be recruited through the PROTECT study database. As a condition of recruiting through this database, the PROTECT team have requested that they are provided with access to research data from the CoCoA-PAD study for participants recruited through PROTECT. We agreed that participants will be provided with information about sharing their data with the PROTECT team and asked to provide their informed consent for this during the consenting process (see PIS and electronic consent form (using REDCap)). If participants agree, their PROTECT participant ID will be added to the research database. This allows for targeted sharing of data, while maintaining the anonymity and confidentiality of the research database.

9.6. Data Protection and Legal Compliance

The study complies fully with UK General Data Protection Regulation (UK GDPR) and the Data Protection Act 2018. University of Plymouth is the Data Controller for research data. University Hospitals Plymouth, NHS Trust, Devon Partnership NHS Trust and NELFT act as Processors for local data collection. The University of Birmingham is a Processor for analysing speech data.

A Data Protection Impact Assessment (DPIA) has been completed. The legal basis for processing data is public interest in scientific research. All data handling procedures reflect NHS data protection standards and University of Plymouth research governance requirements. Although the project includes international collaborators, no personal data will be transferred outside the UK/EEA. Only anonymised datasets may be shared with international collaborators. Therefore, neither an International Data Transfer Agreement (UK) nor a Standard Contractual Clauses (EU) are required.

9.7. Data Breach and Incident Response

In the event of a data breach, the University of Plymouth's Data Protection Officer (DPO) and the study sponsor will be notified immediately. Incidents are triaged by the Sponsor and DPO(s); notifiable personal-data breaches are reported to the Information Commissioner's Office ICO within 72 hours, in line with NHS digital governance protocols. The Research Ethics Committee (REC) will be informed of material confidentiality breaches affecting participant welfare. To mitigate risk, all data access is access controlled and encrypted. Regular back-ups are conducted, and audit trails are maintained for all database activities.

The University of Birmingham and Sheffield Hallam University follow the same breach notification requirements as the platform Processor and will notify the Controllers, via the University of Plymouth, within 24 hours of becoming aware of a personal data breach.

9.8. Use of Digital Tools and Software

Digital platforms used in this research include REDCap, Gorilla Experiment Builder, HearWHO, FrACT, MATLAB, Microsoft Teams, Microsoft SharePoint, and MRI processing software used by BRIC. REDCap will be used for consent, case report forms, study database management, and direct entry of screening and assessment outcomes. Gorilla Experiment Builder will be used to deliver the computerised CoCoA-PAD assessment battery and export pseudonymised task data. HearWHO and FrACT will be used for sensory screening only and will not store direct participant identifiers. One Structure-from-Motion task will be administered locally using MATLAB on a study laptop, with no direct identifiers entered into MATLAB. Audio recordings will be captured via Microsoft Teams. MRI data will be processed through imaging pipelines provided by BRIC. Data analysis will be conducted using SPSS, Jamovi, RStudio, and relevant specialist analysis software.

10. Regulatory Compliance

10.1. Declaration of Helsinki

The CI will ensure that this study is conducted taking into account the principles of the Declaration of Helsinki.

10.2. ICH Guidelines for Good Clinical Practice

This study will be conducted in accordance with the principles of Good Clinical Practice as outlined in ICH E6(R2) and will incorporate evolving best practices consistent with the forthcoming ICH E6(R3) update.

10.3. Human Tissue Act 2004.

The Human Tissue Act 2004 regulates the removal, storage, and use of human tissue for research in the UK. Plasma samples are not classed as 'relevant material' under the Human Tissue Act 2004 because they do not contain intact cells. However, if any cellular material were inadvertently present, the samples would fall under the HTA and be treated accordingly. The following steps will be implemented to reduce this risk:

- Where possible, DAPI staining will be used to clearly identify cellular material and confirm that no cellular material is transferred into the cryovials. Please note, this is not available in all research sites.
- As outlined section 9.3 (blood taking and processing section), the EDTA tube (9ml) will produce approximately 5ml of plasma, which is sufficient for the extraction of 4ml of plasma to be extracted transferred into a two cryovials. This ensures that research nurses and phlebotomists can stay well clear of the buffy layers or cellular material when extracting plasma with the pipette, which reduces the risk of contamination.

The CoCoA-PAD study ensures full compliance by obtaining informed consent from participants for the collection, analysis, and secure storage of plasma samples. Samples will be pseudonymised, tracked, and stored in access-controlled freezers at approved facilities, with appropriate material transfer agreements in place for external analysis. The study operates under NHS Research Ethics Committee approval, which provides the legal basis for temporary storage of samples for research purposes in accordance with The Human Tissue Act 2004 guidelines.

10.4. Data Protection Act and GDPR

All aspects of the CoCoA-PAD study will be conducted in full compliance with the UK General Data Protection Regulation (UK GDPR) and the Data Protection Act 2018. Processing of personal data (voice recordings and cognitive performance) and special-category data (health) is undertaken under UK GDPR Article 6(1)(e) (public task) for NHS sites, and Article 6(1)(f) (legitimate interests) for University of Plymouth, together with Article 9(2)(j) and Data Protection Act 2018 Schedule 1, Part 1(4) for scientific research, with safeguards in line with Article 89(1).

Participants will provide informed consent for the collection, storage, and use of their data. Personal identifiers will be stored separately from research data using pseudonymisation, with access strictly limited to authorised members of the research team. All electronic data will be stored on secure, access-controlled university servers or platforms (e.g. REDCap or SharePoint) with appropriate encryption and audit trails. Data will be retained only for the period specified in the protocol and in line with sponsor and university retention policies. All data processing activities will be overseen by the institution's Data Protection Officer and the study's Chief Investigator.

10.5. Mental Capacity Act 2005

The Mental Capacity Act 2005 (MCA) provides a legal framework for supporting individuals to make decisions and for acting in their best interests if they lack capacity. It applies to adults aged 16 and over in England and Wales. In this study, the MCA is not directly applicable, as having capacity to provide informed consent is an inclusion criterion for participation. Similarly, our recruitment is targeting people with, at worst, *mild* cognitive difficulties with intact functional independence. Therefore, it is very unlikely that their cognitive difficulties would compromise their mental capacity (or indeed whether there would be a legitimate basis to question mental capacity in the absence of a recognised '*impairment or disturbance in the mind or brain*', as specified in the Act. Individuals who lack the mental capacity, as defined by the Mental Capacity Act 2005, will be excluded from participating in this study.

However, to ensure participants have capacity and are making an informed decision, the research team will implement a brief capacity check during the consent process. This will involve asking potential participants to explain in their own words key aspects of the study as outlined in the Participant Information Sheet (PIS), including:

- What the study involves
- Any potential risks or benefits
- Their right to withdraw at any time

This approach ensures the participant has understood the information and can weigh it to make a voluntary and informed decision. If any concerns about capacity arise, and with reasonable adjustments, the potential participant is unable to demonstrate an ability to understand, retain, weigh-up and communicate their decision to participate, they will not be included in the study.

11. Statistical Considerations

11.1. Missing Data

Missing data will be carefully monitored throughout the study. If any data are missing, the research team will first look at how often this happens and whether there is a pattern. If the amount of missing data is small, we may continue with the analysis as planned. If more data are missing, we will use appropriate methods, such regression-based approaches to correct for this. All decisions about how we handle missing data will be agreed with the statistician, and the full

analysis plan, including the procedure for managing missing data, will be pre-registered on the Open Science Framework.

11.2. Discontinue and withdrawal from the study:

Participants are free to discontinue from the study at any time and this will be emphasised during the consent process. If a participant chooses to discontinue during the assessment the session will end immediately. The participant will be asked to provide a reason for their withdrawal, but they do not have to provide a reason. Participants who discontinue with the study will be asked whether they would like the data collected up until that point to be included in the study, or whether they would like to withdraw their data. Data collected on participants prior to discontinuation will be retained for analysis unless the participant requests otherwise.

Participants can withdraw their data from the study at any time without giving a reason. If they choose to withdraw their data, their data will be deleted from the site file and research database. However, once the study database is finalised and the separate personal information file is securely destroyed, which will occur when the database has been finalised, it will no longer be possible to identify individual participants. At that point, their data will be fully anonymised and cannot be withdrawn, in line with ethical and data protection guidelines. This process will be clearly explained in the participant information sheet.

11.3. Sample Size

Given that there are three independent studies, a justification of the proposed sample is outlined for each study.

Study 1: Diagnostic Accuracy of CoCoA-PAD Subtests

The aim of this study is to test whether CoCoA-PAD subtests can distinguish between healthy controls (i.e., people with subjective memory problems without any evidence of AD biomarkers or cognitive decline) and people with preclinical and prodromal Alzheimer's disease. This study uses a prospective research design, and therefore exact participant numbers in each diagnostic criteria cannot be determined until after data collection. Figure 3 provides an estimate of the final sample composition, which includes of 36 healthy controls, 18 people with preclinical AD, and 40 people with prodromal AD. A power calculation using a fixed one-way ANOVA (estimated effect size $f = 0.33$ (moderate effect), $k = 3$) required a minimum sample of 90 to achieve the required power ($\alpha = 0.05$, $1-\beta = 0.8$). Based on current projections (36 controls, 18 preclinical AD, and 40 with prodromal AD), this would be achieved.

Study 2: The relationship between CoCoA-PAD subtests and the health of key brain regions

This study aimed to measure the strength of the association between key brain regions and performance on CoCoA-PAD subtests. It includes a subgroup of study 1 participants. A power calculation using a linear multiple regression (fixed model, single regression coefficient, effect size f^2 (0.1, small) required a minimum sample of 64 participants to achieve the required power ($\alpha = 0.05$, $1-\beta = 0.8$).

Study 3: Testing whether CoCoA-PAD is sensitive to pathological cognitive decline in AD

This study aimed to compare 1 year change score (time 2 score – time 1 score) on CoCoA-PAD subtest scores in people with early Alzheimer’s disease and healthy controls. It includes a subgroup of study 1 participants. A power calculation using a matched pairs *t* test (Cohen’s *d* = 0.5 (moderate)) required a sample of 27 to achieve the required power ($\alpha = 0.05$, $1-\beta = 0.8$).

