4.2. Study 2. Relationship Between Brain Health and CoCoA-PAD Performance

Participants

All participants from Study 1 who live within driving distance of Plymouth ($n=81$) will be invited to undergo a magnetic resonance imaging (MRI) assessment. As such, study 2 will consist of participants who fit into each diagnostic criteria from Study 1.

Sampling

This study will use a convenience sampling procedure based on recruitment to Study 1 and participant location. A cross-sectional design will be employed.

Procedure

Participants will undergo MRI assessment following their participation in Study 1.

Measures

This study will measure the relationship between CoCoA-PAD subtest scores and key indicators of neuronal health. MRI data will be obtained using both single (T1-weighted) and multi-shell imaging approaches.

The specific measures of brain health include:

1. Volumetric measures using T1-weighted imaging of key regions of interest (ROI) associated with early Alzheimer's disease.
2. Diffusion Tensor Imaging (DTI) measures, including Fractional Anisotropy (FA), Radial Diffusivity (RD) and Mean Diffusivity (MD) of defined white matter tracts associated with Alzheimer's disease.
3. Neurite Density Index (NDI), Free Water Fraction (FWF), and Orientation Dispersion Index (ODI) metrics from Neurite Orientation Dispersion and Density Imaging (NODDI) of key grey matter regions of interest.

Figure 3 illustrates the estimated post-diagnostic participant numbers from Study 1.

4.3. Study 3. Measuring the Ability of CoCoA-PAD Subtests at Determining Change Over Time

Participants

A sub-sample of 36 participants from the Study 1 sample will be reassessed on CoCoA-PAD approximately one year after their initial engagement in the CoCoA-PAD study. 18 participants will be selected from both the healthy control and prodromal AD groups.

Sampling

This study will use a criterion based sampling procedure, selecting participants from Study 1 retrospectively based on diagnostic classification.

Procedure

Participants will complete the CoCoA-PAD battery a second time, approximately 11-15 months after their initial assessment.

Measures

The primary outcome measure will be change in scores on CoCoA-PAD subtests (time 2 – time 1 score). This study will therefore use a retrospective (known-group) between-group quasi-experimental research design.

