5.1. Recruitment Sites

This study will run across three research sites: University Hospitals Plymouth NHS Trust, Devon Partnership Trust, and North East London NHS Foundation Trust. Additionally, Cornwall Foundation NHS Trust and Livewell Southwest will be patient identification centres (PICs). Given that this research is funded by the NIHR, it is eligible to be adopted onto the NIHR portfolio, which includes 'service support costs' to recruit through local NHS research teams. Most participants (81) will be recruited through the Plymouth site, and all will be offered an MRI scan. Participants in the other sites will not be offered this scan due to the limited availability of 3 tesla imaging protocols, and the costs associated with delivering MRI scans through the NHS. 19 participants will be recruited through both Devon Partnership NHS Trust and 20 from North East London Foundation NHS Trust. These participants will not be offered an MRI scan. A visual map of the recruitment sites and participant numbers are provided in Figure 4.

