To prevent physical risks, all participants will undergo a standardised MRI safety screening led by trained NHS radiographers before scanning. This includes detailed checks for implants, surgical history, or metallic objects, with exclusion of any participant for whom MRI would be contraindicated. During the scan, participants will be positioned comfortably with the aid of cushions or supports and instructed to inform staff of any discomfort. Noise-cancelling headphones will be provided to reduce scanner noise, along with the option to listen to the radio to improve comfort. The scan will be conducted under the supervision of qualified NHS radiographers, with continuous two-way communication and a panic button available throughout to ensure participant safety and immediate response to any issues.

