11.4. Provisional Data Analysis

The CI will work with a medical statistician, [name], to finalise the data analysis plan, and will publish this on Open Science Framework, prior to the start of data collection. This will ensure both rigour and transparency. A provisional data analysis plan is outlined for each sub-study below. Furthermore, Appendix 2 provides a specific breakdown of the hypotheses and analysis plan for each CoCoA-PAD subtest. This should be considered provisional and may be subject to change prior to the start of the study.

Study 1: Diagnostic Accuracy of CoCoA-PAD Subtests

The aim of this study is to test whether each CoCoA-PAD subtest can distinguish between healthy controls and people with preclinical and prodromal Alzheimer’s disease. This study will use a Welch’s ANOVA to accommodate unequal variances and sample sizes ($k=3$, healthy controls, preclinical AD, and prodromal AD) and Games–Howell post hoc test. A series of receiver operator curves, area under the curves, and optimised sensitivity and specificity values based on Youden index, will be calculated to measure the diagnostic accuracy of each subtest also.

Study 2: The relationship between CoCoA-PAD subtests and the health of key brain regions

Associations between CoCoA-PAD subtest scores and regional brain volume, density and connectivity will first be explored using Spearman correlations, adjusted for false discovery rate using the Benjamini-Hochberg Procedure. Multiple linear regression models will then be used to assess the predictive value of MRI-derived volumetric measures on CoCoA-PAD performance, adjusting for potential confounders including age, sex, education, and intracranial volume. Model fit and assumptions will be evaluated to ensure robustness.

Study 3: Testing whether CoCoA-PAD is sensitive to pathological cognitive decline in AD

Change scores on CoCoA-PAD subtests will be calculated by subtracting time 1 score from time 2 score. As such, negative change scores will denote a decline in performance. A series of *t* tests will be used to test whether the prodromal AD group exhibit higher levels of cognitive decline over a one-year interval. To control for the false discovery rate (FDR) across multiple *t*-tests, the Benjamini–Hochberg procedure was applied with a threshold of $q = 0.05$. This method adjusts *p*-values to reduce the risk of Type I error when conducting multiple comparisons.

Data Analysis Software

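### Study 2's minimum of 64 holds only for an undeclared one-sided test; two-sided it is 81, the whole invited MRI sample, and for one uncorrected test

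*Protocol*

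**What the plan says.** Section 11.3 gives the basis for Study 2 as "A power calculation using a linear multiple regression (fixed model, single regression coefficient, effect size f^2 (0.1, small"), with alpha 0.05 and power 0.8, and concludes that this "required a minimum sample of 64 participants to achieve the required power". It states neither the sidedness of the test nor the number of predictors, and mentions no MRI loss and no multiplicity.

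Section 4.2 says that Study 1 participants "who live within driving distance of Plymouth ($n=81$) will be invited to undergo a magnetic resonance imaging (MRI) assessment". Section 5.1 agrees: "Most participants (81) will be recruited through the Plymouth site, and all will be offered an MRI scan". Table 2 gives 81 as the Study 2 total. Section 7.4 describes MRI safety screening "with exclusion of any participant for whom MRI would be contraindicated".

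Section 11.4 first explores Spearman correlations, "adjusted for false discovery rate using the Benjamini-Hochberg Procedure", and then fits regressions of CoCoA-PAD performance on volumetric measures, "adjusting for potential confounders including age, sex, education, and intracranial volume". Section 4.6 makes a general commitment to false discovery rate correction. Appendix 2 lists primary tracts and regions for each subtest, without expected signs.

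**The concern.** A minimum sample size is the number against which a completed study is judged. If 64 scans were accepted as enough for 80% power, a null association between a subtest and a brain measure could be read as good evidence against an association with a partial correlation of about 0.30. Under ordinary two-sided testing, 64 does not support that reading. This bears on primary objective iii, the relationship between CoCoA-PAD subtests and neurodegeneration.

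Three further features point the same way: the two-sided requirement equals the number invited, with no allowance for people who cannot or will not be scanned; the alpha is that of one test in a study that plans many; and the effect size is called small, although the usual convention for a small f² is 0.02.

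**Working it through.** **Inputs.** From section 11.3: f² = 0.1, alpha = 0.05, power = 0.80, stated N = 64. From section 11.4: four named confounders plus one MRI measure, so about p = 5 predictors; section 11.3 gives no p, so it was varied from 1 to 10. From sections 4.2 and 5.1: 81 invited.

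**Formula.** The test of one coefficient uses a noncentral t distribution with noncentrality √(f²·N) and N − p − 1 degrees of freedom.

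**Reproducing the stated figure (p = 5).**
- N = 64: noncentrality √(0.1 × 64) = 2.530; degrees of freedom 64 − 5 − 1 = 58.
- One-sided critical value 1.672: power 0.804. N = 63 gives 0.798, so 64 is the one-sided minimum.
- Two-sided critical value 2.002: power 0.701.

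**Two-sided requirement (p = 5).**
- N = 81: noncentrality √(0.1 × 81) = 2.846; degrees of freedom 75; critical value 1.992; power 0.802. N = 80 gives 0.797, so 81 is the minimum.

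For every p tried from 1 to 10, the one-sided answer is 64 and the two-sided answer is 81. The unstated number of predictors therefore cannot explain the difference.

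**MRI loss (assumed; the protocol gives no rate).** Two-sided power for one test:

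| Scanned | Lost from 81 | Power |
|---|---|---|
| 81 | 0 | 80% |
| 76 | 5 | 78% |
| 73 | 8 | 76% |
| 69 | 12 | 73% |
| 64 | 17 | 70% |

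**Effect size.** Partial r = √(f²/(1 + f²)) = √(0.1/1.1) = 0.30.

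**Multiplicity (illustration only).** The summary table in Appendix 2 lists primary tracts and regions for 13 subtests. In the table's order from SILT to antisaccade:
- tracts: 4+4+4+3+3+2+3+3+3+4+3+3+3 = 42
- regions: 4+4+5+3+5+3+4+4+3+4+3+4+5 = 51

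With FA, RD and MD for tracts and NDI for regions (Table 2), this is 42 × 3 + 51 = 177 tests. Without Connected Speech, whose diagnostic hypothesis is exploratory, it is 39 × 3 + 48 = 165.

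Benjamini-Hochberg was simulated at q = 0.05 with independent two-sided tests, every true effect having f² = 0.1. Average power over the true effects, with 177 tests:

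| Share of effects that are real | N = 81 | N = 64 |
|---|---|---|
| 10% | 38% | 23% |
| 25% | 53% | 35% |
| 50% | 65% | 49% |
| 75% | 73% | 57% |
| 100% | 77% | 63% |

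With 165 tests the results differ by no more than about two percentage points.

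**The case against.** The strongest reply is that 64 is not an arithmetic slip. It is the correct one-sided answer, and Study 3's 27 in the same section is also one-sided (matched pairs, d = 0.5: one-sided power 0.81 at 27, while two-sided needs 34). This suggests a consistent choice, and directional hypotheses could be defended, because each imaging metric can have its own predicted sign. That stands as an explanation of where 64 came from. It does not rescue the figure: neither section 11.3, section 11.4 nor Appendix 2 states a direction, and section 11.3 describes the aim as measuring the strength of an association.

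The second reply is that the planned 81 meets the two-sided requirement. This is true for one test with every invited person scanned, and it is why the point is not more serious.

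The third concerns multiplicity, and much of it stands. Section 11.4 attaches Benjamini-Hochberg to the exploratory Spearman step, whereas the power calculation is for a regression coefficient, and the regressions are described for volumetric measures, which Appendix 2 marks as secondary. No family is defined for the section 4.6 commitment, q = 0.05 is stated only for Study 3, and section 11.4 is expressly provisional. Defining the family and choosing primary metrics can properly be left to the analysis plan.

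A reader might go further and infer that the protocol claims a surplus of 17 scans, that at least 177 confirmatory tests are fixed, or that corrected power is known to be far below 80%. The documents support none of these. Section 11.3 never compares 64 with 81; 177 is one count and includes an exploratory subtest; and at N = 81 the illustrative corrected power reaches 77% if every effect is real. Nor does the protocol claim power for f² = 0.02: it states 0.1 openly, and only the label is wrong.

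**Conclusion.** The point holds, and should be fixed. The minimum of 64 is right only for a one-sided test that the protocol does not declare. Under conventional two-sided testing the minimum is 81, and 64 gives 70% power. This rests only on the stated f², alpha and power; the one-sided origin is inferred from reproducing the figure.

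The two-sided requirement uses up the whole invited sample. The protocol foresees that some people cannot be scanned, so power below 80% is likely; 73–78% for 69–76 scanned depends on assumed losses.

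The stated 80% is for one unadjusted test, and is lower after false discovery rate correction. The range of about 38–77% at N = 81 is an illustration. It assumes that 10–100% of roughly 165–177 independent tests are true effects, all with f² = 0.1, at q = 0.05. Real tests will be correlated, and the share of true effects is unknown.

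**What to change.** In section 11.3, Study 2:

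- State that tests are two-sided, and replace the minimum of 64 with 81.
- Give power at plausible scanned numbers, for example 80% at 81, 78% at 76, 76% at 73 and 73% at 69, with the expected MRI loss given as an explicit assumption.
- Say that these figures are for a single unadjusted test and that power is lower after false discovery rate correction. The illustrative corrected figures need not be printed.
- Replace the label 'small' with 'f² = 0.1, partial r about 0.30'.

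If one-sided tests are in fact intended, the protocol would have to say so and give the expected direction for each measure; 64 would then stand for a single unadjusted test.

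The cost is protocol wording and a less favourable power statement. The planned sample of 81, the imaging and the choice of metrics need not change.
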